8.1.1.6 Assignment of Screening Number

All consented subjects will be given a unique screening number that will be used to identify the subject for all procedures that occur prior to treatment allocation. Each subject will be assigned only one screening number. Screening numbers must not be re-used for different subjects. Any subject who is screened multiple times will retain the original screening number assigned at the initial screening visit. Once a screening number is assigned to a subject, it can never be re-assigned to another subject.

8.1.1.7 Assignment of Randomization Number

No randomization will be performed and no randomization numbers will be used.

8.1.1.8 Trial Compliance (Medication/Diet/Activity/Other)

As discussed above, if there is any delay in pembrolizumab that would result in patient being unable to undergo surgery within 56-77 days of study initiation (day of first pembrolizumab dose), then patient will go off trial and go directly to surgery.

8.1.2 Clinical Procedures/Assessments

8.1.2.1 Adverse Event (AE) Monitoring

The investigator or qualified designee will assess each participant to evaluate for potential new or worsening AEs as specified in the Trial Flow Chart and more frequently if clinically indicated. Adverse experiences will be graded and recorded throughout the study and during the follow-up period according to NCI CTCAE Version 5.0 (see [Appendix 2](#)). Toxicities will be characterized in terms regarding seriousness, causality, toxicity grading, and action taken with regard to trial treatment.

Please refer to [Section 8.2](#) for detailed information regarding the assessment and recording of AEs.

8.1.2.2 Full Physical Exam

The investigator or qualified designee will perform a complete physical exam during the screening period and at all times as indicated on the study flow chart. Clinically significant abnormal findings should be recorded as medical history. A full physical exam should be performed during screening,

8.1.2.3 Vital Signs

The investigator or qualified designee will take vital signs at screening, prior to the administration of each dose of trial treatment and at all other times points as specified in the Trial Flow Chart ([Section 7.0](#)). Vital signs should include temperature, pulse, respiratory rate, weight and blood pressure. Height will be measured at screening only.

8.1.2.4 Eastern Cooperative Oncology Group (ECOG) Performance Scale

The investigator or qualified designee will assess ECOG status (see [Appendix 1](#)) at screening, prior to the administration of each dose of trial treatment and discontinuation of trial treatment as specified in the Trial Flow Chart.

8.1.2.5 Tumor Imaging and Assessment of Disease

CT scans of chest, abdomen, and pelvis with IV and PO contrast will be obtained at baseline during the screening period, after 3 doses of pembrolizumab (day 56 ± 3 days), post-operatively (42-70 days post-operatively) and subsequently according to standard of care surveillance (annually for two years post-surgery and then as clinically indicated). Response will be assessed by institutional radiologists using RECIST 1.1. If a reason exists precluding use of iodinated contrast, MRI abd/pelvis and noncontrast chest CT can be substituted.

8.1.2.5.1 Initial Tumor Imaging

Initial tumor imaging at screening must be performed within 28 days prior to the date of allocation. CT scans of chest, abdomen, and pelvis with IV/PO contrast will be obtained at baseline. If a reason exists precluding use of iodinated contrast, MRI abd/pelvis and noncontrast chest CT can be substituted. PET/CT will also be required at baseline. Finally, EUS will be required at baseline as per this institution's standard of care to confirm staging. Baseline diagnostic laparoscopy is not mandated and can be performed if clinically indicated.

8.1.2.5.2 Tumor Imaging During the Study

The first on-study imaging assessment (CT chest/abdomen/pelvis with IV/PO contrast) should be performed at 8 weeks (56 days ± 3 days) from the date of allocation. PET/CT, EUS, and upper endoscopy will also be performed at this time. Subsequent tumor imaging (CT chest/abdomen/pelvis with IV/PO contrast) should be performed 6-10 weeks post-operatively. Thereafter, surveillance imaging will be performed as per standard of care at this institution (annually for 2 years post-surgery and then as clinically indicated). Scans will be evaluated for progression or new lesions as per RECIST 1.1. If a reason exists precluding use of iodinated contrast, MRI abd/pelvis and noncontrast chest CT can be substituted. Surveillance EGD will only be performed as clinically indicated.

8.1.2.5.3 End of Treatment and Follow-up Tumor Imaging

In participants who discontinue study treatment without documented disease progression, every effort should be made to continue monitoring their disease status by tumor imaging using the same imaging schedule used while on treatment (6-10 weeks after surgery, then annually to year 2, and then as needed) to monitor disease status until the start of a new anticancer treatment, disease progression, pregnancy, death, withdrawal of consent, or the end of the study, whichever occurs first.

8.1.2.5.4 RECIST 1.1 Assessment of Disease

RECIST 1.1 will be used as the primary measure for assessment of tumor response, date of disease progression/recurrence, and as a basis for all protocol guidelines related to disease status (eg, discontinuation of study treatment).

8.1.2.5.5 iRECIST Assessment of Disease

iRECIST is based on RECIST 1.1, but adapted to account for the unique tumor response seen with immunotherapeutic drugs. When clinically stable, participants should not be discontinued until progression is confirmed by the Investigator, working with local radiology, according to the rules below. This allowance to continue treatment despite initial radiologic PD takes into account the observation that some participants can have a transient tumor flare in the first few months after the start of immunotherapy, and then experience subsequent disease response.

A description of the adaptations and iRECIST process is provided in [Appendix 4](#), with additional detail in the iRECIST publication. [45] iRECIST will be used by the Investigator to assess tumor response and progression/recurrence, and make treatment decisions.

8.1.2.6 Tumor Tissue Collection and Correlative Studies Sampling

Patients will undergo tumor and blood collection as per routine clinical practice and will be consented to IRB 16294A prospective protocol for all indicated correlatives.

Tissue specimens collected at diagnosis and at time of surgical resection will be obtained per standard-of-care (SOC) practices. As per SOC at this institution, tissue at diagnosis and/or at time of surgical resection (if tumor is still present) will undergo testing for MSI via immunohistochemistry (IHC), HER2 testing (via IHC and/or fluorescence in situ hybridization (FISH)), and Epstein-Barr encoding region in situ hybridization (EBER ISH). These specimens will also undergo PD-L1 CPS testing, whole-exome RNAseq expression, as well as NGS testing via Foundation One CDx™ (Foundation Medicine, Cambridge, MA). ctDNA using Guardant360 (Guardant Health, Redwood, CA) will be evaluated before pembrolizumab therapy, after pembrolizumab therapy, after surgery, and at time of recurrence (if applicable) as per SOC.

Finally, patient fecal microbiomes will be characterized using fecal 16S RNA sequencing before pembrolizumab therapy, after pembrolizumab therapy, after surgery, and at time of recurrence (if applicable) as discussed below.

8.1.2.6.1 Fecal 16S RNA Sequencing

At least 3 aliquots of stool will be stored at -80°C in tubes from the UltraClean® Fecal DNA Isolation Kits (MoBio). This technique uses a bead-beating method and removes inhibitors of PCR enzymatic reactions. Backup samples will be stored in a 50ml tubes. We will characterize the intestinal microbiota by MiSeq deep sequencing of bacterial 16S rRNA. Following assessment of genomic DNA quality and concentration, 16S rRNA-based tag sequence

libraries will be generated from an evolutionarily conserved gene marker to obtain deep surveys of the microbial communities present using next generation sequencing. The 16S rRNA-based Illumina library preparation and data analysis PCR primers to be used are specific for the 515-806 base pair V3-V4 region of the 16S rRNA encoding gene (338F: 5'-GTGCCAGCMGCCGCGTAA-3' and 806R: 5'-GGACTACHVGGGTWTCTAAT-3') and contain Illumina 3' adapter sequences as well as a 12-base pair barcode. This barcode-based primer approach allows sequencing of multiple samples in a single sequencing run without the need for physical partitioning. Sequencing will be performed by the Next Generation Sequencing Core at Argonne National Laboratory using an Illumina MiSeq. Sequences will then be trimmed and classified with the QIIME toolkit. Using the QIIME wrappers, OTUs are picked at 97% sequence identity using *uclust* and a representative sequence is then chosen for each OTU by selecting the most abundant sequence in that OTU. These representative sequences are classified and assigned a taxonomic string using the RDP Classifier. PyNAST-aligned sequences are used to build a phylogenetic tree with FastTree for calculation of unweighted/weighted UniFrac distances (as well as other measures of diversity) for ecological analyses, including visualization via ordination (e.g. principal coordinates analysis). Furthermore, the transformation of sequence data into a numerical format (abundance of each OTU) allows the application of a variety of ecologic metrics to characterize the samples individually (measures of α -diversity) as well as between sample comparisons (measures of β -diversity). A comparison of frequencies of specific sequences in patients having a T cell-inflamed versus non-T cell-inflamed tumor microenvironment will be performed, and also comparisons between clinical responders versus non-responders. Rarefaction curves will be used to evaluate and compare OTU richness between libraries. Diversity indices, including the Shannon diversity index, and richness estimators (Chao1 and ACE) will be calculated.

8.1.2.6.2 Initial Screening Endoscopy

All subjects must receive an initial screening endoscopy at the site enrolling the subject. If the subject has received an endoscopy per standard of care prior to joining the study and the endoscopy was conducted at the enrolling study site, the subject does not have to repeat the procedure. Tissue samples collected from standard of care endoscopies can be accepted at screening only if the endoscopy was conducted at the enrolling institution.

If the subject received an endoscopy prior to joining the study at a non-enrolling site, a new endoscopy must be conducted at the enrolling site and will be considered part of clinical research.

8.1.3 Laboratory Procedures/Assessments

Details regarding specific laboratory procedures/assessments to be performed in this trial are provided below.

Laboratory tests for hematology, chemistry, urinalysis, and others are specified in Table 5.

Table 5 Laboratory Tests

Hematology	Chemistry	Urinalysis	Other
Hematocrit	Albumin	Blood	Serum β -human chorionic gonadotropin†
Hemoglobin	Alkaline phosphatase	Glucose	(β -hCG)†
Platelet count	Alanine aminotransferase (ALT)	Protein	Total triiodothyronine (T3)
WBC (total and differential)	Aspartate aminotransferase (AST)	Specific gravity	Free thyroxine (T4)
Red Blood Cell Count	Lactate dehydrogenase (LDH)	Microscopic exam (If abnormal)	Thyroid stimulating hormone (TSH)
Absolute Neutrophil Count	Carbon Dioxide ‡	results are noted	Carcinoembryonic antigen (CEA)
Absolute Lymphocyte Count	(CO_2 or bicarbonate)	Urine pregnancy test †	Carbohydrate antigen 19-9 (CA 19-9)
	Uric Acid		Blood for correlative studies
	Calcium		Stool for correlative studies
	Chloride		PT/INR
	Glucose		aPTT
	Phosphorus		
	Potassium		
	Sodium		
	Magnesium		
	Total Bilirubin		
	Direct Bilirubin (If total bilirubin is elevated above the upper limit of normal)		
	Total protein		
	Blood Urea Nitrogen		

† Perform on women of childbearing potential only. If urine pregnancy results cannot be confirmed as negative, a serum pregnancy test will be required.

‡ If considered standard of care in your region.

8.1.4 Other Procedures

8.1.4.1 Withdrawal/Discontinuation

When a participant discontinues/withdraws prior to trial completion, all applicable activities scheduled for the final trial visit should be performed at the time of discontinuation. Any adverse events which are present at the time of discontinuation/withdrawal should be followed in accordance with the safety requirements outlined in Section 8.2 - Assessing and Recording Adverse Events.

8.1.4.2 Blinding/Unblinding

Not applicable as this is an open label study.

8.1.5 Visit Requirements

Visit requirements are outlined in [Section 7.0](#) - Trial Flow Chart. Specific procedure-related details are provided above in [Section 8.1](#) - Trial Procedures.

8.1.5.1 Screening

8.1.5.1.1 Screening Period

The screening period is 28 days during which laboratory and imaging studies prior to treatment must be completed. See flow chart, [Section 7.0](#) for further details.

8.1.5.2 Treatment Period

8.1.5.3 Post-Treatment Visits

8.1.5.3.1 Safety Follow-Up Visit

Safety assessments will be performed at each physician visit. This includes on day 21 ± 3 , day 42 ± 3 , day 56 ± 3 , and 42-70 days post-operatively.

The mandatory Safety Follow-Up Visit will be conducted approximately 14 days after the last dose of study treatment (on day 56 ± 3). All AEs that occur prior to the Safety Follow-Up Visit should be recorded. Participants with an AE of Grade > 1 will be followed until the resolution of the AE to Grade 0-1 or until the beginning of a new anti-cancer therapy, whichever occurs first. SAEs that occur within 90 days of the end of treatment (end of treatment is the day of last dose of pembrolizumab) or before initiation of a new anti-cancer treatment should also be followed and recorded.

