2.0 TRIAL DESIGN

2.1 Trial Design

This is a prospective, single-arm phase IIa study enrolling patients with cT1b-2N0Mx esophageal and gastric adenocarcinoma. Patients will receive 3 cycles of pembrolizumab 200mg intravenously on day 1 of a 3-week cycle. After 3 cycles, patients will undergo surgery. The target surgery date is 8-11 weeks after the first dose of pembrolizumab. Surgical approach will vary based upon tumor location but would entail tumor resection with either D2 or two-field lymphadenectomy. The primary objective is to determine the pathologic complete response (pCR) rate in patients with cT1b-T2N0 gastroesophageal adenocarcinoma (GEA) treated with neoadjuvant pembrolizumab followed by surgical resection. A sample size of 33 patients will provide 90% power with one-sided alpha 0.1 to detect a pCR rate of 15% using neoadjuvant pembrolizumab. Secondary endpoints include R0 resection rate, safety and tolerability, disease-free survival (DFS), and overall survival (OS). Diagnostic tissue biopsy and surgical resection specimen pre- and post-pembrolizumab therapy will be assessed for panel DNA/RNA next generation sequencing (NGS), programmed death-ligand 1 (PD-L1) combined positive score (CPS) testing, Epstein-Barr virus (EBV) testing, microsatellite instability (MSI) testing and tumor mutation burden (TMB). Plasma circulating tumor DNA (ctDNA) samples will be collected for panel NGS (73 gene in real time, and more stored for larger 550 gene and smaller higher depth panels) prior to pembrolizumab therapy, after neoadjuvant pembrolizumab therapy but prior to surgery, after surgery, and upon recurrence if/when this occurs. Stool samples will also be obtained at these time points and subjected to Fecal 16S RNA seq.

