6.7 Clinical Criteria for Early Trial Termination

Early trial termination will be the result of the criteria specified below:

1. Quality or quantity of data recording is inaccurate or incomplete with $\geq 10\%$ of data unavailable.
2. Poor adherence to protocol and regulatory requirements
3. Incidence or severity of adverse drug reaction in this or other studies indicates a potential health hazard to participants
4. Plans to modify or discontinue the development of the study drug
5. If patient deaths or excessive toxicity attributed to the investigational drug are seen in the 30 days following surgery. A **30-day post-operative** death rate of $\geq 5\%$ attributed to study agent is considered unacceptable. The relationship of the investigational drug to the mortality will be determined by the treating medical oncologist and surgeon.

In the event of Merck decision to no longer supply study drug, ample notification will be provided so that appropriate adjustments to participant treatment can be made.

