8.2 Assessing and Recording Adverse Events

An adverse event is defined as any untoward medical occurrence in a patient or clinical investigation participant administered a pharmaceutical product and which does not necessarily have to have a causal relationship with this treatment. An adverse event can therefore be any unfavorable and unintended sign (including an abnormal laboratory finding, for example), symptom, or disease temporally associated with the use of a medicinal product or protocol-specified procedure, whether or not considered related to the medicinal product or protocol-specified procedure. Any worsening (i.e., any clinically significant adverse change in frequency and/or intensity) of a preexisting condition that is temporally associated with the use of the Merck's product, is also an adverse event.

Changes resulting from normal growth and development that do not vary significantly in frequency or severity from expected levels are not to be considered adverse events. Examples of this may include, but are not limited to, teething, typical crying in infants and children and onset of menses or menopause occurring at a physiologically appropriate time.

Merck product includes any pharmaceutical product, biological product, device, diagnostic agent or protocol-specified procedure, whether investigational (including placebo or active comparator medication) or marketed, manufactured by, licensed by, provided by or distributed by Merck for human use.

Adverse events may occur during the course of the use of Merck product in clinical trials, or as prescribed in clinical practice, from overdose (whether accidental or intentional), from abuse and from withdrawal.

All AEs, SAEs and other reportable safety events that occur after the consent form is signed but before treatment allocation/randomization must be reported by the investigator if the participant is receiving placebo run-in or other run-in treatment, if the event caused the

participant to be excluded from the study, or is the result of a protocol-specified intervention, including but not limited to washout or discontinuation of usual therapy, diet, or a procedure.

- All AEs from the time of treatment allocation/randomization through 30 days following cessation of study treatment must be reported by the investigator.

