9.0 STATISTICAL ANALYSIS PLAN

9.1 Statistical Analysis Plan Summary

9.2 Statistical Analysis Plan

At our institution, patients with cT1b-2N0M0 GEA typically undergo surgery alone without additional therapy. Thus, we expect 100% of resected specimens to have evidence of cancer in historical controls. We hypothesize that neoadjuvant pembrolizumab will result in a pCR rate (Grade 1a+1b) of 15%. A sample size of 33 patients will provide 90% power with one-sided alpha 0.1 to detect this pCR rate using neoadjuvant pembrolizumab. More specifically, we will use an optimal, Simon two-stage design to test the null hypothesis that the Grade 1 response rate is 1% vs. the alternative that it is 15%. Fifteen patients will be enrolled in the first stage and if no complete pathological responses are observed the trial will be terminated for futility. If one or more responses are seen, an additional 18 patients will be studied for a total of 33. Two or more responses in 33 patients will indicate that the treatment is promising, whereas 0/15 or 1/33 will be considered a negative result. Patients who receive pembrolizumab but do not go to surgery will be counted as not having achieved a pCR.

We will also assess activity in the subset of patients who are PD-L1 positive. Assuming an approximate PD-L1 positivity incidence (CPS score ≥ 1) of 50% of all patients enrolled, this sample size of 16 expected PD-L1 positive patients will provide over 95% power with one-sided alpha 0.05 to detect a pCR rate (Grade 1a+1b) of 30% vs. 1% using neoadjuvant pembrolizumab in this preplanned subset. Using a higher CPS cutoff of ≥ 10 we assume 20% of patients will be PD-L1 positive based on recent data, and the sample size of 7 expected PD-

L1 positive patients will provide 67% power with one-sided alpha 0.05 to detect a pCR rate (Grade 1a+1b) of 30% vs. 1%

Complete responses (R0) will be tabulated along with an exact 90% confidence interval. DFS and OS will be estimated using the Kaplan-Meier method. Adverse events will be summarized by type, grade, and attribution to the study drug.

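### For non-serious adverse events, Section 8.1.5.3.1 (to day 56 ± 3) is out of line with Section 8.2 (to day 72), and neither period covers the 30 post-operative days named in termination criterion 5

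*Combined protocol and SAP*

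**What the plan says.** Section 8.1.5.3.1 schedules a mandatory Safety Follow-Up Visit about two weeks after the last dose, on day 56 ± 3. It then states: "All AEs that occur prior to the Safety Follow-Up Visit should be recorded". AEs above Grade 1 are followed to Grade 0-1 or to new anticancer therapy. SAEs are carried to 90 days after the last dose, which the section defines as the end of treatment. The section also lists a safety assessment 42-70 days after surgery.

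Section 8.2 sets a different limit: "All AEs from the time of treatment allocation/randomization through 30 days following cessation of study treatment must be reported by the investigator". It gives SAEs 90 days, shortened to 30 days if new anticancer therapy starts.

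Section 8.1.2.1 says "Adverse experiences will be graded and recorded throughout the study and during the follow-up period" and then sends the reader to Section 8.2 for the detail of AE assessment and recording.

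On timing, Section 2.1 says: "The target surgery date is 8-11 weeks after the first dose of pembrolizumab". Section 6.2.2 gives the same window as days 56-77.

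Criterion 5 in Section 6.7 opens: "If patient deaths or excessive toxicity attributed to the investigational drug are seen in the 30 days following surgery". The analysis in Section 9.2 is one sentence, "Adverse events will be summarized by type, grade, and attribution to the study drug", with no start or end date.

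**The concern.** Safety and tolerability of pembrolizumab is a secondary objective (Section 3.2). The two sections that put a date on non-serious AE collection give different dates, and surgery is planned for the weeks around them. A site that takes the Safety Follow-Up Visit as the cut-off would stop collecting new non-serious events at about the time of the operation. A site that follows Section 8.2 would collect some post-operative days for a patient operated on early and none for a patient operated on late. Counts could then differ between patients because of scheduling and site practice, and Section 11 provides for more than one participating institution.

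The post-operative month matters to this protocol. Section 6.2.2 warns that immune-related events can appear months after dosing ends, and criterion 5 looks at drug-attributed toxicity in the 30 days after surgery. Section 8.2.4 evaluates grade and seriousness separately, so a Grade 3 event need not be an SAE.

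**Working it through.** **Inputs.** Doses every 3 weeks for three cycles (Section 6.2): days 0, 21 and 42, counting the first dose as day 0. Dosing window ± 3 days (Section 6.2.1). Surgery on day S, with S from 56 to 77 (Sections 2.1 and 6.2.2). End of treatment is the last dose (Section 8.1.5.3.1).

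**The plan's own figure.** Visit = last dose + 14 = 42 + 14 = day 56, as stated. With ± 3 days the visit falls on days 53-59.

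**Section 8.2 limit for all AEs.** 42 + 30 = day 72. If dose 3 is 3 days early or late, this becomes day 69 or day 75.

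**Gap between the two sections.** 72 − 56 = 16 days nominally; 72 − 59 = 13 to 72 − 53 = 19 across the visit window.

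**Post-operative days inside the Section 8.2 period.** max(0, 72 − S), to be set against the 30 days in criterion 5:

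| Surgery day S | Days covered, of 30 | 30-day point (S + 30) |
|---|---|---|
| 56 | 16 | 86 |
| 63 | 9 | 93 |
| 70 | 2 | 100 |
| 72 | 0 | 102 |
| 77 | 0 | 107 |

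If recording stopped at the Safety Follow-Up Visit, coverage would be 0 days, or at most 59 − 56 = 3 days if surgery on day 56 came before a visit on day 59.

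**Early stopping.** After dose 1 only, the Section 8.2 limit is 0 + 30 = day 30. After dose 2 it is 21 + 30 = day 51. Both come before day 56, so no post-operative day would be covered if surgery still took place on days 56-77.

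**Next listed safety assessment.** 42-70 days after surgery: days 98-126 for S = 56 and days 119-147 for S = 77. Each range begins after the 30-day point.

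**SAEs.** 42 + 90 = day 132. The latest 30-day post-operative point is 77 + 30 = day 107, so the SAE period contains it. If new anticancer therapy starts, the SAE limit in Section 8.2 becomes 30 days after the last dose, day 72 on schedule.

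**The case against.** The strongest reply is that the texts are ordered and nested. Section 8.1.2.1 is a general statement about grading that defers to Section 8.2. Section 8.1.5.3.1 does not say that recording stops at the visit, so a site that meets the 30-day rule meets both sections. The listed assessment 42-70 days after surgery fits poorly with a day-56 cut-off. Section 6.4.1 also uses 30 days after the last dose for concomitant medications. A period tied to the last dose is a legitimate choice when the objective is the safety of the drug.

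Much of this stands. A reader might infer three rival rules, one of them requiring every AE to be recorded for up to five years after surgery. The documents do not support that, because Section 8.1.2.1 points to Section 8.2. A reader might also infer that serious post-operative toxicity would be missed or that criterion 5 could not operate. That is not supported either. SAEs run to day 132, an event that prolongs hospitalization counts as serious (Section 8.2.4), drug-related SAEs are reportable at any time (Section 8.2), and safety is reviewed weekly (Sections 8.2.6 and 11.4). The only number in criterion 5 is a death rate.

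Two things remain. The nested reading leaves Section 8.1.5.3.1 naming an earlier date than Section 8.2 and extending only SAEs past it, which invites a site to stop early. And accepting Section 8.2 as the governing rule does not remove the dependence on surgery date. The AE rows of the flow chart are not visible in the text available and could not be checked; its visible footnotes give no AE period.

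**Conclusion.** The concern holds in limited form. Section 8.1.5.3.1 is out of line with Section 8.2 by about 16 days. Under the governing Section 8.2 rule, new non-serious AEs are covered for between 16 and 0 of the 30 post-operative days, according to when surgery takes place. That does not match the period in criterion 5, and Section 9.2 does not settle which period is to be summarized.

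The figures assume three doses on schedule with dose 3 on day 42. A 3-day shift in dose 3 moves the day-72 limit by 3 days. The documents give no AE rate, so the number of events affected cannot be stated. The primary endpoint, sample size and error rates are untouched. Severity: minor.

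**What to change.** In Section 8.1.5.3.1, remove the Safety Follow-Up Visit as the end point for AE recording and adopt the Section 8.2 rule. In both sections state: *all AEs are recorded to 30 days after the last dose or 30 days after surgery, whichever is later; for a patient who has no surgery, to 30 days after the last dose; SAEs as in Section 8.2.* On schedule, recording then ends on max(72, S + 30), that is, day 86 for S = 56 and day 107 for S = 77. Keep the visit itself. Section 8.1.2.1 needs no change, since it already refers to Section 8.2. In Section 9.2, summarize AEs separately before and after surgery.

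The cost is wording in three sections and one AE review 30 days after surgery, by telephone or from the surgical record, for at most 33 patients. Extending collection past surgery is a design choice that goes further than aligning the two sections. It will bring surgical events not caused by the drug into the AE table, and the planned attribution summary and the split at surgery keep them apart.
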